##### **9.4.6.2 Determination of Dose Volume**

Pegloticase will be administered as an admixture of 8 mg in 250 mL of 0.45% or 0.9% Sodium Chloride Injection, United States Pharmacopeia (USP) for IV infusion.

In the event of an IR, the infusion should be slowed, or stopped, and restarted at a slower rate at the discretion of the Investigator. Infusions subsequent to an IR in an individual subject may be given in a larger volume of diluent, not to exceed 500 mL. In this case, the infusion duration will also be extended to a minimum of 3 hours.

### **9.4.6.3 Details Concerning Timing and Dose Administration**

#### **9.4.6.3.1 Preparation and Administration**

##### **9.4.6.3.1.1 Preparation**

Vials of pegloticase will be visually inspected for particulate matter and discoloration before administration, whenever solution and container permit. Vials will not be used if either is present. Using appropriate aseptic technique, 1 mL of pegloticase will be withdrawn from the vial into a sterile syringe. Any unused portion of product remaining in the vial will be discarded. Syringe contents will be injected into a single 250 mL bag of 0.45% or 0.9% Sodium Chloride Injection, USP for IV infusion and will not be mixed or diluted with other drugs. The infusion bag containing the dilute pegloticase solution will be inverted a number of times to ensure thorough mixing but will not be shaken. In accordance with good pharmacy practice, gloves will be worn during preparation of the dose.

Pegloticase must be started within 4 hours of dilution. Before administration, the diluted solution of pegloticase will be allowed to reach room temperature. Pegloticase must never be subjected to artificial heating.

##### **9.4.6.3.1.2 Dose and Administration**

###### **Methotrexate**

During the MTX Tolerability Assessment Period (Week -6 until the Week -4 visit), all subjects will take MTX 15 mg orally weekly.

At the Week -4 visit, subjects who tolerated methotrexate will be randomized to receive MTX 15 mg or placebo for MTX orally weekly. Subjects will be blinded to MTX or placebo for MTX beginning at Week -4 through the remainder of the study. Subjects will continue to take the blinded MTX or placebo for MTX during the Run-in Period (from Week -4 to Day 1) at the 15 mg MTX dose or placebo for MTX dose. Investigators may choose to have subjects take the weekly dose divided over the day (i.e. BID, TID). If a subject does not tolerate the 15 mg MTX or placebo for MTX dose after randomization at the Week -4 Visit and prior to Day 1, the MTX or placebo for MTX may be dose-reduced or discontinued based on pre-specified criteria and after discussion with the Sponsor medical monitor. The subject will be allowed to remain in the study. After Day 1, MTX or placebo for MTX may be re-initiated. The subject will be re-initiated to the same treatment they were randomized to at Week -4, however the dose may be adjusted (See [Section 9.4.6.3.2.2](#)). The re-initiated MTX or placebo for MTX will remain blinded to the subject. During the Run-in Period, if a dose is missed, it should be taken as soon as it is remembered. If it is within 48 hours of the next scheduled dose, the subject will be instructed to skip the missed dose and resume at the next regularly scheduled time; thus, subjects will be instructed not to double a dose to make up for a missed dose if within 48 hours of the next dose.

During the Pegloticase + IMM Period, subjects will be instructed to take MTX or placebo for MTX weekly on the same day each week, within 1 to 3 days prior to each pegloticase infusion and one additional weekly dose after the last infusion for subjects who have not stopped pegloticase due to

sUA stopping rules; however, if a subject does not do so, MTX or placebo for MTX must be taken  $\geq 60$  minutes prior to each pegloticase infusion. Investigators may choose to have subjects take the weekly dose divided over the day (i.e. BID, TID). The total MTX or placebo for MTX dose should be taken within 24 hours, preferably the same calendar day each week, with the date and time of each dose recorded in the dosing calendar. If a subject becomes unable to tolerate the MTX or placebo for MTX during the Pegloticase + IMM Period, the dosage may be decreased.

Refer to [Section 9.4.12](#) for contraception requirements.

Subjects will take folic acid 1 mg orally every day beginning at Week -6 (the start of MTX) until prior to the Week 52 Visit.

Due to the recent availability of several effective vaccines for COVID-19, study subjects may elect to be vaccinated. The American College of Rheumatology (ACR) has issued guidelines on the use of immunomodulatory therapy such as MTX in subjects who receive COVID-19 vaccines [Mikuls TR et al., 2020a; 2020b; 2021; ACR COVID-19 Vaccine Clinical Guidance Task Force, 2021]. This guidance should be referenced and followed for subjects who are vaccinated for COVID-19 while on study and treated with MTX or placebo for MTX. Due to the rapidly expanding information and evolving evidence related to COVID-19, which may lead to modification of some guidance statements over time, updated versions of this guidance will be published, with the version number included in the title. Investigators should ensure that they are consulting the most current version.

### **Pegloticase**

All subjects will receive pegloticase at the same dose of 8 mg administered IV every 2 weeks for a total of 26 infusions from Day 1 through the Week 50 Visit (Pegloticase + IMM Period). Subjects will not be fasting on the day of infusion and will be encouraged to have a snack or normal meal before or after the infusion. Pre-infusion sUA results must be reported by the local or central laboratory prior to pegloticase infusion (see [Section 9.5.1.1](#)).

Standardized IR prophylaxis consisting of pre-treatment with antihistamines, acetaminophen, and corticosteroids will accompany each infusion (see [Section 9.4.1.3](#)). The drug name, dose, and timing of these prophylactic medications will be recorded.

Pegloticase will be administered as an admixture of 8 mg in 250 mL of 0.45% or 0.9% Sodium Chloride Injection, USP for IV infusion by gravity feed or infusion pump. Pegloticase will not be administered as an IV push or bolus.

In a patent IV site, using tubing with no in-line filter, the pegloticase preparation will be infused over approximately  $120 \pm 15$  minutes while the subject is under close observation for any signs of distress. If an in-line filter is used, it should be 0.2  $\mu\text{m}$  or larger. At the end of the infusion, the IV line will be flushed with 10 mL of normal saline to ensure the full dose is administered. The date and time of infusion start and stop (inclusive of the IV flush) will be recorded.

#### **9.4.6.3.2 Dose Modifications, Interruptions, and Delays**

##### **9.4.6.3.2.1 Pegloticase Modifications**

Infusion of pegloticase will be immediately held if the subject experiences any significant IR such as respiratory distress, agitation, chest or back pain, urticaria, or another clinically significant event occurring during infusion. If the AE meets the definition of an SAE for IR, the infusion should not be restarted unless the site Investigator determines it is safe to resume the infusion. If the AE does not meet the definition of an SAE for IR, the site Investigator may make the decision to re-start the infusion depending upon the nature and severity of the AE.

Infusions subsequent to an IR in an individual subject may be given in a larger volume of diluent, not to exceed 500 mL. In this case, the infusion duration will also be extended to a minimum of 3 hours. The total volume and duration of infusion will be captured in the medical record and eCRF.

Infusion of pegloticase may be held or delayed if the subject has an ongoing SAE or AE/SAE that occurs just prior to the infusion. The status of subjects with skipped infusions will be discussed with the Investigator and the Sponsor's Medical Monitor on a case-by-case basis to determine whether the subject should continue to the next scheduled infusion or proceed to the End of Pegloticase Visit.

##### **9.4.6.3.2.2 MTX/Placebo for MTX Dose Titration Algorithm and Intolerance Criteria**

During the MTX Tolerability Assessment Period subjects will be considered a screen failure if any of the following new laboratory findings or symptoms reflecting MTX intolerance occur:

1. Abnormal Hematology findings:
  - a. WBC  $< 3.5 \times 10^9/L$
  - b. Platelets  $< 75 \times 10^9/L$
  - c. Hematocrit  $< 32\%$
2. Abnormal hepatic function findings:
  - a. AST/ALT  $> 1.5 \times$  upper limit of reference range and
  - b. Albumin  $<$  lower limit of reference range
3. Abnormal renal function: eGFR  $< 30 \text{ ml/min}/1.73 \text{ m}^2$  (as estimated with the MDRD equation).
4. New clinically important signs and symptoms, such as the following:
  - a. Rash or oral ulceration
  - b. Persistent nausea, vomiting and diarrhea
  - c. New or increasing dyspnea or dry cough, or unexplained cough with fever
  - d. Severe sore throat, abnormal bruising
  - e. Severe headaches, fatigue, and problems concentrating

Note that repeat laboratory tests may be needed to confirm these new findings. In addition, if minor clinical symptoms emerge, such as mild stomatitis, mild GI discomfort, etc., the investigator may increase folic acid dose (e.g. 2 mg daily) or recommend a divided dose of MTX (e.g. 3 tabs of 2.5

mg in the morning and evening on the day of dosing); if symptoms improve, the subject will not be considered a screen failure on the basis of that symptom.

During the Run-In and Pegloticase+IMM Period, MTX or placebo for MTX dose guidance based on new laboratory findings or new symptoms is as follows:

| Lab Parameters                           | Value                                      | MTX or placebo for MTX Dose Change |
|--|--|------------------------------------|
| WBC                                      | $3.0 \times 10^9/L \sim 3.5 \times 10^9/L$ | Decrease to 10 mg                  |
|  | $< 3.0 \times 10^9/L$                      | Temporary stop                     |
| Platelets                                | $< 50 \times 10^9/L$                       | Temporary stop                     |
| Hematocrit                               | $< 27\%$                                   | Temporary stop                     |
| AST/ALT                                  | Between $1.5 \sim 2 \times ULN$            | Decrease to 10 mg                  |
|  | $> 2 \times ULN$                           | Temporary stop                     |
| eGFR                                     | $< 30 \text{ ml/min}/1.73 \text{ m}^2$     | Temporary stop                     |
| New clinically important symptoms/signs* | Yes  | Temporary stop                     |

\* New clinically important symptoms or important medical events:

- a. Rash or oral ulceration
- b. Persistent nausea, vomiting and diarrhea
- c. New or increasing dyspnea or dry cough, or unexplained cough with fever
- d. Severe sore throat, abnormal bruising
- e. Severe headaches, fatigue, and problems concentrating
- f. Any other important medical events that might increase methotrexate toxicity or predispose to new or worsening infection (e.g. undergoing surgery, hospitalization, being treated with antibiotics, having a clinical infection, developing new clinically significant pericardial / pleural effusion or ascites)

Note that if minor clinical symptoms emerge, such as mild stomatitis, mild GI discomfort, etc., the investigator may increase folic acid dose to 2 mg daily or recommend a divided dose of MTX or placebo for MTX (e.g. 3 tabs of 2.5 mg in the morning and evening on the day of dosing) and monitor for symptom resolution.

Investigators should discuss the emergence of any one of the following criteria with the medical monitor to review the case:

1. ALT/AST > 1.5 x ULN on 3 of any 5 consecutive measures
2. Albumin < 0.8 x LLN on 2 consecutive measures
3. Any laboratory or clinical symptoms leading to temporary stop on 3 consecutive measures, in which case the medical monitor will review to consider re-initiation, a continued temporary stop, or a permanent stop in discussion with the PI.

Guidance for increasing MTX or placebo for MTX back towards 15 mg after dose reduction, based on improvement or resolution of abnormal liver enzymes ( $>2 \times$  upper limit of normal):

1. When liver enzymes return to values  $\leq 1.5 \times$  upper limit of normal, increase MTX or placebo for MTX dose by 2.5 mg and reassess in 2 weeks.
2. If liver enzymes remain  $\leq 1.5 \times$  upper limit of normal, increase MTX or placebo for MTX dose by 2.5 mg and reassess in 2 weeks.

Improvement of other laboratory abnormalities potentially attributed to MTX or placebo for MTX may also warrant titration back up to 15 mg weekly, based on PI judgement and in discussion with the Sponsor medical monitor.

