## **9 INVESTIGATIONAL PLAN**

### **9.1 Overall Study Design and Plan**

This study is a Phase 4, multicenter, randomized, double-blind, placebo-controlled, parallel-group, efficacy and safety study of pegloticase with MTX vs. pegloticase with placebo for MTX in adult subjects with uncontrolled gout.

The study design will include: 1) a Screening Period (screening should be completed within 6 weeks prior to Week -6); 2) a 2-week MTX Tolerability Assessment Period consisting of 2 weeks oral MTX for all subjects; 3) a Run-In Period consisting of randomization followed by 4 weeks of blinded oral MTX or placebo for MTX; 4) a 52-week Pegloticase + IMM Period; 5) a Safety Follow-up (Phone/Email/Site Visit) and 6) a 3 and 6 month Post Treatment Follow-up.

All subjects who meet eligibility criteria at Screening will begin 15 mg MTX orally weekly at the Week -6 visit. Subjects will also take folic acid 1 mg orally every day beginning during the MTX Tolerability Assessment Period (Week -6 to Week -4) and continuing until prior to the Week 52 Visit.

Subjects must be able to tolerate the weekly dose of MTX 15 mg for 2 weeks to be eligible to be randomized at Week -4. Subjects who are unable to tolerate the 15 mg dose of MTX during the 2 weeks preceding the Week -4 visit during the Run-in Period will be considered screen failures.

Subjects who tolerate the weekly 15 mg MTX dose during the 2 weeks preceding Week -4 Visit and continue to meet eligibility criteria will be randomized at the Week -4 Visit in a 2:1 ratio (stratified by presence of tophi) to receive either blinded oral 15 mg MTX or blinded oral

placebo for MTX. Tophi presence (yes, no) will be based on presence of at least one tophus identified by the Investigator. Subjects will continue to take the blinded MTX or placebo for MTX from Week -4 to Day 1 (the Run-in period) at the 15 mg MTX or placebo for MTX dose. If a subject does not tolerate the 15 mg MTX or placebo for MTX dose after randomization at the Week -4 Visit and prior to Day 1, the MTX or placebo for MTX may be dose-reduced or discontinued based on pre-specified criteria and after discussion with the Sponsor medical monitor. The subject will be allowed to remain in the study. After Day 1, MTX or placebo for MTX may be re-initiated. The subject will be re-initiated to the same treatment they were randomized to at Week -4. The re-initiated MTX or placebo for MTX will remain blinded.

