### 9.3.2 Exclusion Criteria

Subjects will be ineligible for study participation if they meet **any** of the following criteria:

1. Weight  $>160$  kg (352 pounds) at Screening.
2. Any serious acute bacterial infection, unless treated and completely resolved with antibiotics at least 2 weeks prior to the Week -6 Visit.
3. Severe chronic or recurrent bacterial infections, such as recurrent pneumonia or chronic bronchiectasis.
4. Current or chronic treatment with systemic immunosuppressive agents such as MTX, azathioprine, or mycophenolate mofetil; prednisone  $\geq 10$  mg/day or equivalent dose of other corticosteroid on a chronic basis (3 months or longer) would also meet exclusion criteria.
5. History of any transplant surgery requiring maintenance immunosuppressive therapy.
6. Known history of hepatitis B virus surface antigen positivity or hepatitis B DNA positivity.
7. Known history of hepatitis C virus RNA positivity.
8. Known history of Human Immunodeficiency Virus (HIV) positivity.
9. Glucose-6-phosphate dehydrogenase deficiency (tested at the Screening Visit).
10. Chronic renal impairment defined as estimated glomerular filtration rate (eGFR)  $<40$  mL/min/1.73 m^2 or currently on dialysis.
11. Non-compensated congestive heart failure or hospitalization for congestive heart failure within 3 months of the Screening Visit, uncontrolled arrhythmia, treatment for acute

coronary syndrome (myocardial infarction or unstable angina), or uncontrolled blood pressure ( $>160/100$  mmHg) prior to Randomization at Week -4.

- 12. Pregnant, planning to become pregnant, breastfeeding, planning to impregnate female partner, or not on an effective form of birth control, as determined by the Investigator.
- 13. Prior treatment with pegloticase, another recombinant uricase (rasburicase), or concomitant therapy with a polyethylene glycol-conjugated drug.
- 14. Known allergy to pegylated products or history of anaphylactic reaction to a recombinant protein or porcine product.
- 15. Contraindication to MTX treatment or MTX treatment considered inappropriate.
- 16. Known intolerance to MTX.
- 17. Receipt of an investigational drug within 4 weeks or 5 half-lives, whichever is longer, prior to MTX administration at Week -6 or plans to take an investigational drug during the study.
- 18. Liver transaminase levels (AST or ALT)  $>$  upper limit of normal (ULN) or albumin  $<$  the lower limit of normal (LLN) at the Screening Visit.

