#### **9.5.4.7 Clinical Laboratory Safety Tests**

Blood (for hematology and clinical chemistry) will be collected at the Screening, Week -6 (prior to the first dose of MTX), and Week -4 and -2 Visits during the Run-in Period; prior to pegloticase infusion on Day 1 and at the Weeks 2, 6, 14, 22, 24, 36 and the non-infusion End of Pegloticase Infusions Visit (if applicable), Week 52/End of Study/Early Termination and 3 and 6 month Post Treatment Follow-up Visits.

Blood and urine samples (for allantoin) will be collected prior to the pegloticase infusion and after the end of each pegloticase infusion prior to discharge from the site on Day 1 and at Weeks 14, 24 and 36; Additional blood and urine samples for allantoin will be collected at the non-infusion End of Pegloticase Infusions Visit (if applicable) and the Week 52/End of study/Early Termination Visit. If subject consent, subject's allantoin samples will be retained for potential future analyses which may include biomarkers relevant to gout (e.g. inflammatory markers) or gout co-morbidities in response to pegloticase or other potential treatments for gout. The samples will be retained no longer than 15 years after study completion or as required by applicable law. The samples will be stored in a secured storage space with adequate measures to protect confidentiality.

Urine (for albumin:creatinine ratio) samples will be collected prior to the pegloticase infusion on Day 1 and at the Weeks 14, 24, 36 and the non-infusion End of Pegloticase Infusions Visit (if applicable) and Week 52/End of Study/Early Termination Visits.

Urine (for human chorionic gonadotropin) samples will be collected at all visits except the Screening Visit and Weeks 21, 23 and 3 and 6 month Post Treatment Follow-up Visits for all female subjects of childbearing potential.

Safety laboratory assessments will include:

- Hematology: complete blood count with differential (hemoglobin concentration, hematocrit, erythrocyte count, platelet count, leukocyte count, and differential leukocyte count)

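### The methotrexate tolerability rule joins raised AST/ALT and low albumin with 'and'; change it to 'or' so that either finding alone is a screen failure

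*Protocol*

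**What the plan says.** **Purpose of the tolerability period.** Protocol 9.1 requires subjects to be "able to tolerate the weekly dose of MTX 15 mg for 2 weeks to be eligible to be randomized at Week -4".

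**Screen-failure rule.** Protocol 9.4.6.3.2.2 makes a subject a screen failure "if any of the following new laboratory findings or symptoms reflecting MTX intolerance occur". In item 2, the first limb is AST/ALT above 1.5 times the "upper limit of reference range and"; the second limb is albumin below the lower limit. A note below the list allows repeat tests to confirm new findings.

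**Dose table.** For the Run-In and Pegloticase + IMM Periods, the same section states that "MTX or placebo for MTX dose guidance based on new laboratory findings or new symptoms is as follows". AST/ALT between 1.5 and 2 times the ULN means a cut to 10 mg, and above 2 times a temporary stop. The table has no albumin row.

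**Related hepatic criteria.** Exclusion 18 (Protocol 9.3.2) joins its two limbs the other way, "upper limit of normal (ULN) or albumin", but applies only at the Screening Visit. The matters to be raised with the medical monitor after randomisation list the enzymes and albumin separately, the latter as "Albumin < 0.8 x LLN on 2 consecutive measures".

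**Sampling.** Under Protocol 9.5.4.7, chemistry is drawn "at the Screening, Week -6 (prior to the first dose of MTX), and Week -4 and -2 Visits" and again on Day 1. It is analysed centrally, with local testing if needed. Protocol 9.5.8.1.3 places the eligibility check, the blood draw and randomisation all at the Week -4 visit.

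**The concern.** The tolerability period exists so that only subjects who can take 15 mg of MTX are randomised. If the hepatic item needs both findings, a subject whose transaminases have risen well past the limit, but whose albumin is normal, counts as tolerant. That subject can be randomised and then meets a dose-cut or stop rule on the same laboratory value.

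Three things are at stake. The first is consistency: approximately 65 sites could apply an eligibility rule in two ways. The second is safety, since a subject with an enzyme rise that the protocol itself treats as a reason to stop would be admitted. The third is the per-protocol population, which requires 15 mg of MTX or placebo at the first pegloticase dose (Protocol 9.6.2, SAP 5.4); a subject reduced or stopped in the Run-In Period may miss that condition.

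**Working it through.** The plan gives no figure for this point, so the check sets the rules side by side. I take the upper limit of the reference range in item 2 and the ULN in the dose table to be the same number.

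**Step 1. Apply each reading to the same subjects.** The AST/ALT multiples are test values chosen to fall in each band of the dose table. They say nothing about frequency.

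| AST/ALT (x ULN) | Albumin | Item 2 read as *and* | Item 2 read as *or* | Dose table |
|---|---|---|---|---|
| 1.0, 1.4 | normal | pass | pass | no action |
| 1.0, 1.4 | low | pass | screen failure | no action |
| 1.6, 1.9 | normal | **pass** | screen failure | **10 mg** |
| 1.6, 1.9 | low | screen failure | screen failure | 10 mg |
| 2.5, 5 | normal | **pass** | screen failure | **temporary stop** |
| 2.5, 5 | low | screen failure | screen failure | temporary stop |

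Under *and*, 4 of the 12 combinations pass tolerability while already meeting a dose-table action: all four multiples above 1.5 with normal albumin. Under *or*, none does. The two combinations that *or* fails without a matching dose-table action (1.0 and 1.4 with low albumin) are those that exclusion 18 would also reject at Screening.

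**Step 2. Compare the other laboratory items in the same section.**

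| Item | Tolerability limit | Dose-table action limit |
|---|---|---|
| WBC (x 10^9/L) | < 3.5 | 3.0 to 3.5: 10 mg; < 3.0: stop |
| Platelets (x 10^9/L) | < 75 | < 50: stop |
| Haematocrit | < 32% | < 27%: stop |
| eGFR (mL/min/1.73 m²) | < 30 | < 30: stop |

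In all four the tolerability limit is equal to or stricter than the action limit, apart from a WBC of exactly 3.5. The hepatic item is looser only under the *and* reading; under *or* it falls in line. This comparison therefore supports *or* as the likely intent but does not prove that the text means *and*.

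**Step 3. Find the sample on which the rule can act.** Scheduled chemistry up to Day 1 is at Screening, Week -6 (before the first dose), Week -4, Week -2 and Day 1. Randomisation is at Week -4. One scheduled sample, Week -4, is therefore taken on MTX and no later than the randomisation visit. The Week -4 procedures require eligibility to be confirmed but do not say that this result must be in hand first.

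**Step 4. Check the primary analysis.** The stated power is 88% for 90 versus 45 subjects at 71% versus 43%, two-sided alpha 0.05. The pooled proportion is (45 x 0.43 + 90 x 0.71)/135 = 0.617. The null SE is √(0.617 x 0.383 x (1/45 + 1/90)) = 0.0888, and the alternative SE is √(0.43 x 0.57/45 + 0.71 x 0.29/90) = 0.0879. Power = Φ((0.28 - 1.96 x 0.0888)/0.0879) = 88.6%, which agrees. No input depends on item 2: screen failures occur before randomisation and do not enter the 135.

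**The case against.** **The list reading.** The strongest reply is that this is a drafting slip. The lead-in makes any one finding sufficient, and the same list uses *and* loosely elsewhere: the gastrointestinal symptom item names nausea, vomiting and diarrhoea, and nobody would demand all three. Read that way, item 2 agrees with exclusion 18, with the separate medical-monitor triggers and with the table's first action limit, and no mismatch remains. This stands in part. A reader might infer that the sponsor deliberately chose to require both findings; the documents do not support that. They support only that the text permits it.

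**Other gates.** Eligibility is re-confirmed at Week -4, and an investigator who sees 2.5 times the ULN can rely on inclusion 8, exclusion 15 (MTX inappropriate) or exclusion 25 (undue risk). This also stands in part. Those routes rest on judgement and carry no enzyme threshold, so what is missing is the automatic trigger, not every safeguard.

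**The Week -4 result.** A reader might infer that subjects are randomised without anyone looking at their on-treatment chemistry. That goes too far. Only subjects who still meet the criteria may be randomised, and the on-treatment laboratory limits cannot be applied on schedule without this sample, so review is largely implied. Local testing is already allowed, and randomisation details sit in a procedures manual that is not among the documents. An explicit sentence is a clarification, not the repair of a proven gap.

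**Consequence.** A reader might also infer a biased treatment comparison. The rise in question occurs before randomisation, while every subject takes MTX. The primary analysis includes all randomised subjects, and the per-protocol analysis is a supplemental repeat (SAP 9.2.4). The dose table manages affected subjects after randomisation, and Protocol 9.1 keeps them in the study.

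**Conclusion.** The concern holds as a minor wording fault in a stated eligibility rule. On the literal reading, AST/ALT above 1.5 times the upper limit, even above 2 times, with normal albumin does not fail tolerability but does trigger a dose cut or stop under the same section. On the list reading there is no conflict. A rule that supports both readings should be settled.

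The number of subjects affected is not in the documents and I do not estimate it. Nor can losses from the per-protocol set be derived from the re-escalation guidance ("increase MTX or placebo for MTX dose by 2.5 mg and reassess in 2 weeks"): it covers only recovery from enzymes above 2 times the ULN, and the dose at which to restart after a stop is not stated.

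The ITT primary analysis and the stated power are unaffected, and no imbalance between arms is claimed. The gain is uniform eligibility across sites, a small improvement in patient safety, and possibly fewer subjects lost from a supplemental analysis. The conclusion assumes that the two sections refer to the same upper limit and that the procedures manual does not already settle the matter.

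**What to change.** Change one word in Protocol 9.4.6.3.2.2 item 2, so that it reads in substance: *AST or ALT above 1.5 x the upper reference limit, or albumin below the lower reference limit; repeat the test to confirm if needed.* Keep the albumin limb. Dropping it would loosen the rule for anyone who already reads item 2 as a list, whereas *or* matches exclusion 18.

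As a clarification, add to the Week -4 procedures (9.5.8.1.3) that the Week -4 chemistry result, central or local as 9.5.4.7 already allows, is reviewed when eligibility is confirmed and before randomisation.

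The cost is a short amendment with IRB approval and a note to sites. Expect a few more screen failures, including some for isolated low albumin at sites that had read the rule as *and*. The rescreening and retesting allowed in 9.3.4.3 soften this. Some sites may need a local test or a short wait for the central result.

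The change helps only subjects not yet randomised, and the documents do not give enrolment status. If randomisation is complete, the useful remaining step is to record how sites applied the rule.
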